3 * Describe the duration of an individual participant's participation in the study:

Duration of participation for subjects will be for 2 years following enrollment.

Due to enrollment still ongoing, participation will extend for another two visits after their 2 year follow-ups have been completed for already enrolled patients. Until all follow-up for all enrolled patients is complete, we will continue to see patients on a yearly basis and administer cognitive functioning battery. Also, for patients who have already completed their follow-up, we will ask if they are agreeable to also submitting a blood sample for genetic testing and obtain that if they are willing to continue to be followed.

**With regards to the planned additional follow-up, subjects will be invited to participate in one additional follow-up visit that will be approximately two hours in duration.

4 * Describe the duration of the entire study:

Study timeline

Overall, the project will require approximately 4 years to complete; separated into four major activities. The first year will be devoted to planning, IRB application, and commencing data acquisition. We anticipate an early start to data collection since our center has an established recruitment and treatment infrastructure in place. The projected duration of patient recruitment is 2 years. Follow-up will begin immediately after recruitment, and those patients who entered as late as month 24 will be followed until conclusion of the trial.

**With regards to the planned additional follow-up, the entire duration of the study will be one year.

5 * Describe any additional participant requirements:

Original ACCOF protocol: Quality of life questionnaires will have to be completed by the participant.

**With regards to the planned additional follow-up, there will be no additional participant requirements other than those listed above in question 1.

ID: VIEW4E0280585B400
Name: v2_Study Procedures

View: v2_Sample Size and Data Analysis

Sample Size and Data Analysis

If you uploaded a separate research protocol document in the 'Research Protocol' page, cite the applicable section and page numbers from that document in the answer boxes below.

1 * Provide the rationale and sample size calculations for the proposed target population:

Statistical Analysis

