The PI will oversee recruitment of potential participants, collection and storage of study data, regulatory deadlines and data analysis. This will be accomplished primarily through a standing weekly meeting with research team members. The PI will also meet individually with the study coordinator weekly or as needed to discuss recruitment and any safety issues related to data collection.
- 2 * **Describe the facilities where research procedures are conducted:**
All patient's will be consented at the VA Medical Center. They will also complete neurocognitive testing, questionnaires, and phlebotomy at the VA Medical Center. Participants will be escorted to the vascular lab at the University of Maryland Medical Center to complete imaging and walking and balance assessments. Patient's recruited from the University of Maryland Medical Center will be escorted to the VA Medical Center for consenting, neurocognitive testing, questionnaires, and phlebotomy.

For the purpose of the additional follow-up planned; patients will undergo ultrasound testing, physical function testing and questionnaires at the University of Maryland Medical Center vascular lab.
- 3 * **Describe the availability of medical and/or psychological resources that subjects might need as a result of anticipated consequences of the human research:**
All efforts will be made to ensure subjects are seen safely and efficiently. Reasonable time will be allotted for each subject to complete testing. All procedures will be conducted by trained professionals in the areas of phlebotomy, neuropsychology, and vascular imaging. The PI is available by phone and pager at all times.
- 4 * **Describe the process to ensure that all persons assisting with the research are adequately informed about the protocol, the research procedures, and their duties and functions:**
The PI will speak with all research team members to discuss the study (purpose and procedures) and their role within the study. A standard of practice document will be completed and placed in the research office outlining all procedures of the study. Protocol and study related topics are discussed regularly at a weekly ACCOF conference with all team members.

ID: VIEW4DF83CB976400
Name: v2_Resources

View: v2_Sites Where Research Activities Will Be Conducted

Sites Where Research Activities Will Be Conducted

- 1 * **Is this study a:**
 Multi-Site
 Single Site

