2 * Is this study a clinical trial OR will this study be registered at ClinicalTrials.gov?

A clinical trial is a research study in which one or more human subjects are prospectively assigned to one or more interventions (which may include placebo or other control) to evaluate the effects of those interventions on health-related

biomedical or behavioral outcomes.

Yes No

ID: VIEW4E0280569E000
Name: v2_Type of Research

View: v2_Lay Summary

Lay Summary

1 * Provide a summary of the background and purpose of the study in language that can be understood by a person without a medical degree.

Carotid artery stenosis is a recognised cause of Stroke and/or TIAs(mini stroke). Under appreciated is the fact that the consequence of carotid stenosis may be a slow impairment in thinking, learning, memory and problem solving without evidence of stroke or TIAs.

The goal of this study is to measure the magnitude of cognitive impairment , its impact on the quality of life and its pathophysiology in patients with asymptomatic carotid stenosis.

**With regards to the planned additional follow-up, the goal is to assess how carotid-stenosis-induced cognitive impairment may or may not impact physical function.

ID: VIEW4E02805CF7000
Name: v2_Lay Summary

View: v2_Justification, Objective, & Research Design

Justification, Objective, & Research Design

If you uploaded a separate research protocol document in the 'Research Protocol' page, cite the applicable section and page numbers from that document in the answer boxes below.

1 * Describe the purpose, specific aims, or objectives of this research. State the hypothesis to be tested:

The goal of this proposal is to perform a systematic, adequately powered study to measure the magnitude of cognitive impairment in asymptomatic carotid stenosis, its impact on quality of life, and its potential pathophysiological mechanisms. Information from this study will define an unsuspected morbidity of carotid stenosis and identify subsets of patients at risk for cognitive impairment. It will form the foundation for future studies on prevention, pre-emptive treatment, or rehabilitation of patients with carotid stenosis. It will also improve the selection of patients with carotid stenosis to decrease unnecessary revascularization procedures.

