Carotid artery plaques are known to cause stroke. Cognitive impairment is an insidious but poorly understood problem in patients with carotid plaques. Cognitive function describes how we perform mental processes such as thinking, learning and problem solving. Asymptomatic carotid plaques may affect ≥ 1 million veterans who may be at risk for cognitive impairment. In this study, we will uncover the extent of cognitive impairment in veterans with carotid stenosis who are currently labeled "asymptomatic". Programs to prevent or mitigate cognitive impairment will depend on identifying the mechanisms by which this occurs. We will use sophisticated 3D imaging techniques developed by our group to measure the structure and composition of plaques, number of particles breaking off from them, blood levels of chemicals that could disrupt them, and blood flow restriction to the brain from them. This will help identify patients at risk for cognitive impairment who may benefit from preventative measures and improve selection of patients to decrease unnecessary surgical procedures.

**With regards to the planned additional follow-up, the goal is to assess how carotid-stenosis-induced cognitive impairment may or may not impact physical function.

We hypothesize that participants with carotid stenosis will demonstrate impaired physical function at baseline, increased deterioration of physical function on follow-up evaluation, and reduced response to balance training.

2 * Discuss the research design including but not limited to such issues as: probability of group assignment, potential for subject to be randomized to placebo group, use of control subjects, etc.:

RESEARCH DESIGN & METHODS

This is a prospective longitudinal controlled single-center clinical study designed to measure the extent of cognitive impairment associated with asymptomatic carotid stenosis, potential mediators of impairment, and the functional impact of the resulting disability

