Specific Aim 3 will determine the impact of cognitive impairment on quality of life measures (Short Form-36 and Frenchay activities index). We will test whether at 2 years, regardless of plaque features, cognitive impairment will correlate with a reduction in health-related quality of life scores.

**With regards to the planned additional follow-up, all subjects enrolled in the study will be eligible to participate. They will be contacted to come on ONE day for 2 hours to undergo carotid ultrasound testing, physical function testing, and to answer a questionnaire.

3 * Describe the relevant prior experience and gaps in current knowledge. Describe any relevant preliminary data:

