Tromso study	7/7/2010 11:41 AM	7/7/2010 11:41 AM
CREST REVIEW	7/7/2010 11:41 AM	7/7/2010 11:41 AM
Endarectomy for symptomatic carotid artery stenosis	7/7/2010 11:40 AM	7/7/2010 11:40 AM

3 * Provide a list of 3 keywords or search terms (1 per line) relevant to your research that would help potential participants find your study using search engines:

Keyword 1: Carotid

Keyword 2: Cognition

Keyword 3: Plaque

ID: VIEW4E02805A7E400
Name: v2_Supporting Literature

View: v2_Study Procedures

Study Procedures

If you uploaded a separate research protocol document in the 'Research Protocol' page, cite the applicable section and page numbers from that document in the answer boxes below. (If this study is a collaborative UM/VA study please list each procedure that is being conducted and the locations where it is being conducted.)

1 * Describe all procedures being performed for research purposes only (these procedures would not be done if individuals were not in the study) and when they are performed, including procedures being performed to monitor subjects for safety or to minimize risks:

The schedule for major evaluation components is provided in Table II of the protocol page 32

The time required to obtain the information is provided in Table III of the protocol page 32.

To assess the stated endpoints, our study will establish for each patient, the baseline demographics, vascular risk factor profile, neurologic status (history, neurologic examination, NIHSS), cognitive function (cognitive function tests), plaque information (3D B-mode imaging), microembolic counts (TCD testing), inflammatory status (serum pro-inflammatory markers), perfusion status (cerebrovascular reactivity) and quality of life (SF36, Frenchay index). To assess change in status we will measure for each patient,

follow-up cognitive function, plaque information, microembolic counts, inflammatory status, perfusion status, and quality of life, at 1 and 2 years post-recruitment. The stenosis-free control subjects will undergo an ultrasound carotid assessment at baseline (to rule out stenosis), and assessments of cognitive function at baseline and at 1 and 2 years post-recruitment.

**With regards to the planned additional follow-up, participants will attend one session of approximately 2 hours duration.

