Assessment of physical function including tests of balance and gait. Include the Berg Balance Scale-7 item (BBS), the Dynamic Gait Index-4 item (DGI), the Four Square Step Test and Short Physical Performance Battery. Questionnaires related to balance and walking function will include the Activities-specific Balance Confidence (ABC) Scale, Falls Efficacy Scale. Overall mental health will be assessed using the Mini-mental State Exam questionnaire and activity level will be assessed with the Physical Activity Scale for Elderly (PASE). Carotid Ultrasonography will be used to assess carotid artery blockage. This test is non-invasive and is being performed per clinical standard of care. Patients will remain comfortably recumbent on a stretcher during the testing period. It is extremely unusual for patients to experience any discomfort during the testing. Every effort will be made to explain the test and ensure patient comfort during testing.

2 * Describe all procedures already being performed for diagnostic or treatment purposes (if not applicable to the study, enter "N/A"):

Cognitive function testing

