Conduct of testing. In Specific Aim 1 the primary hypothesis is that in patients with asymptomatic carotid stenosis ($\geq 50\%$ diameter-reducing) who survive stroke-free for 2 years; change in overall and domain-specific cognitive function will be significantly different compared to those without stenosis (fig 1 and 3). The primary analysis of impact will be the overall and domain-specific cognitive change score at 2 years, with the initial score at recruitment serving as the baseline. Patients and control subjects will undergo a 50-minute neurocognitive battery at 3 time points: baseline, 1 year, and 2 years after recruitment. Baseline testing will take place within a few days of recruitment. Following the approach of our prelim data #3 for performing cognitive testing in a similar patient population, the battery will consist of 10 standardized neuropsychological tests for multiple cognitive domains selected on the basis of the NIH harmonization standards, our own preliminary data #3, and published experience in patients with carotid stenosis^{5-10, 31}. All tests have published age-adjusted norms. All participants will undergo all 10 tests. The order of test administration will remain constant for baseline and follow-up evaluations. Tests will be conducted in a quiet room. The order of administration accommodates the delays required for recall intervals and minimizes stimuli interference in memory tasks.

Plaque architecture and composition

The architecture and composition of plaques may influence the risk and quantity of atheroembolization, and the nature and extent of microembolic cerebral injury (fig 1). Specific Aim 2a of our study will investigate whether cognitive impairment is mediated by plaque features that predispose it to rupture and atheroembolization. Specifically, we will test whether A) at 2 years, carotid plaque architecture and composition will independently predict a change in cognitive function and, B) at 2 years, patients with asymptomatic carotid stenosis who develop cognitive impairment will differ in these characteristics compared with similar patients that remain unchanged.

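### Exploratory additional follow-up: the balance-training and deterioration hypotheses cannot be tested as described, and poorer function in stenosis has no matching analysis (minor)

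*Combined protocol and SAP*

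**What the plan says.** The stated purpose of the add-on (Lay Summary; Justification, Objective, & Research Design, item 1) is general: "the goal is to assess how carotid-stenosis-induced cognitive impairment may or may not impact physical function". The hypothesis that follows in the design section has three parts. Stenosis participants are expected to have impaired physical function at baseline, "increased deterioration of physical function on follow-up evaluation, and reduced response to balance training".

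The visit is described as a single occasion. Item 2 of the same section says that "all subjects enrolled in the study will be eligible to participate" and asks them to come on one day for two hours. Study Procedures, item 1, says "participants will attend one session of approximately 2 hours duration", and item 3 again speaks of one extra visit. The performance tests are given in Study Procedures, item 1 ("Include the Berg Balance Scale-7 item (BBS), the Dynamic Gait Index-4 item (DGI), the Four Square Step Test and Short Physical Performance Battery") and again in Testing, item 1, under the additional follow-up. For the original study, the procedures for controls are narrower: "The stenosis-free control subjects will undergo an ultrasound carotid assessment at baseline (to rule out stenosis), and assessments of cognitive function" at baseline, 1 and 2 years.

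One line points the other way. In Resources, item 2, the general paragraph on facilities says participants are escorted to the university vascular lab "to complete imaging and walking and balance assessments". A separate paragraph then covers the additional follow-up.

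The analysis (Sample Size and Data Analysis, item 2) is a standard correlation of previously obtained cognitive scores with the new physical function scores. Item 1 says no direct sample size calculation is possible. Citing a strong relationship in patients without stenosis, it expects to identify or exclude the relationship with about 150 patients.

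**The concern.** A hypothesis, the measurements behind it and the analysis that answers it should line up. Here they do not. One clause needs an intervention that is not described. One needs repeated measurements that are not listed. The third needs a comparison between groups that is not planned.

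At stake is the add-on's ability to answer its own question. As written, a report would have to drop two hypotheses, and any stenosis-versus-control comparison would be chosen after the data are in. The planned correlation serves the general goal, but no adjustment is stated, and age could affect both cognitive and physical scores.

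**Working it through.** **Step 1. Each hypothesis against what is described.**

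| Clause | What it needs | What the document gives |
|---|---|---|
| Reduced response to balance training | A training programme, with measurement around it | The hypothesis sentence is the only mention. Study Procedures item 1, Testing item 1 and Research Related Risks list tests, questionnaires and ultrasound. Study Procedures item 5 says there are no further participant requirements. |
| Greater deterioration | At least two measurements of the same function | Gait and balance tests are listed for the single visit only. The original test lists (Surveys/Questionnaires item 1, Testing item 1) contain none. The extended yearly visits (Study Procedures item 3) name the cognitive battery. |
| Impaired function in stenosis | A comparator and a group comparison | Controls are eligible, since all enrolled subjects may take part and will be contacted (also Recruitment item 1). The patient-versus-control analysis in Sample Size and Data Analysis item 2 covers cognitive change only. |

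If baseline means the additional visit, no second measurement follows it.

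**Step 2. Time at the visit.** Stated durations in minutes are: physical activity questionnaires 20, cognitive health 5, Short Physical Performance Battery 10, four gait and balance tests 20 to 40, ultrasound 20. The sum is 75 to 95 of about 120 minutes. None is assigned to training.

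**Step 3. The Resources line.** The gait and balance forms (Testing item 3) and the new questionnaires (Surveys/Questionnaires item 2) were all uploaded on 6/9/2017. The cognitive battery was uploaded in August 2010. The follow-up consent forms are dated June 2017. The line therefore probably entered with the later amendment. This is not proof, because the schedule table cited in Study Procedures item 1 is not in the supplied text.

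**Step 4. What the planned correlation can show.** The plan gives no figure to reproduce. The only input from the plan is n of about 150; two-sided 5% is assumed because no level is stated for this part. By Fisher's z:

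- Detectable r = tanh[(1.960 + z_power)/√(n − 3)].
- n = 150, 80% power: tanh(2.802/12.124) = 0.227. At 90% power: tanh(3.242/12.124) = 0.261.
- 95% interval at an observed r of 0: ± tanh(1.960/12.124) = ±0.160.
- If only 100 attend (assumption): tanh(2.802/9.849) = 0.277 with 80% power, and ±0.196.

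Adjustment costs little. With 10 covariates (age, sex, education, mood, the four vascular risk factors, time since the battery, group) the divisor becomes √(150 − 3 − 10) = 11.705, and the detectable partial r at 80% power is tanh(2.802/11.705) = 0.235.

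**Step 5. The missing group comparison.** The stenosis:control split is not given. By the normal approximation, the detectable difference at 80% power is 2.802 × √(1/n1 + 1/n2) SD. An assumed 75:75 split gives 0.46 SD, and an assumed 120:30 split gives 0.57 SD. If only stenosis patients attend, no comparison is possible.

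**The case against.** The strongest reply is about weight. The document calls this part an exploration, its general goal is cognition against physical function, and the planned correlation matches that goal. Deleting two clauses repairs most of the problem. This stands, and it is why the point is minor.

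Four stronger readings are tempting, and the documents do not support them.

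- *The study's aims are compromised.* They are not. Aims 1 to 3 use neither the gait and balance tests nor this visit.
- *Deterioration is certainly untestable.* The Resources line and the missing schedule table leave a small opening, so confirmation is needed before the clause is deleted. Self-reported change might also be pieced together for stenosis patients from the earlier SF-36 and the SF-12 at this visit. No such analysis is planned, and neither is a gait or balance test.
- *About 150 people are too few.* The plan's expectation concerns a strong relationship, and 150 can detect or exclude one. Only small correlations remain open.
- *The correlation is necessarily distorted by age.* For the cognitive battery the protocol says "All tests have published age-adjusted norms", so the scores used may be normed; this is not stated for this analysis. Adjusting for age covers either case.

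Controls are also meant to be age-matched with similar vascular risk profiles, which helps a group comparison. But attendance is voluntary, so the balance may not carry over to those who come.

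**Conclusion.** The concern holds for the exploratory follow-up only, at minor severity. The balance-training hypothesis cannot be tested. Deterioration on gait and balance tests cannot be tested either, provided no earlier measurements exist, which the upload dates make likely. Poorer function in stenosis is testable cross-sectionally but has no analysis. The planned correlation answers the general goal without adjustment. At n = 150 and two-sided 5% it detects r of about 0.23 with 80% power, and leaves about ±0.16 open at an observed r of 0. These figures assume that all of the approximately 150 attend. It is also unclear who they are: the sample size text speaks of stenosis patients, whereas eligibility covers everyone enrolled.

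**What to change.** 1. **Justification, Objective, & Research Design, item 1.** Delete the balance-training clause. Confirm that the walking and balance assessments in Resources, item 2, belong to the additional visit. Delete the deterioration clause unless earlier gait and balance data are confirmed; if they are, name the change analysis. Restate the rest as: at the additional visit, participants with carotid stenosis have poorer physical function than controls, and lower cognitive scores are associated with poorer physical function.
2. **Sample Size and Data Analysis, item 2.** If controls attend, add a stenosis-versus-control comparison of physical function adjusted for age, sex and vascular risk factors. Beside the correlation, add a regression of physical function on the earlier composite cognitive score. Adjust it for age, education and mood (the covariates the protocol already names for Aim 1), and for sex, vascular risk factors, time since the battery, and group if both groups attend.
3. **Sample Size and Data Analysis, item 1.** State how many of the approximately 150 are stenosis patients and how many are controls. Replace the claim to identify or exclude the relationship with estimation and a 95% confidence interval, giving the n = 150 figures above and saying that a small correlation cannot be excluded.

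The cost is wording plus analysis of data already planned, with no extra visit or procedure. The downside is a narrower stated objective, and an imprecise group comparison if few controls attend.
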